8.7 Withdrawal and replacement of subjects

8.7.1 Withdrawal of patients

Subjects have the right to withdraw completely or partially from the study at any time and for any reason without prejudice to their future medical assistance by the doctor or the center.

Withdrawal of full consent from a study means that the subject does not wish to receive further investigational treatment, nor does it wish or is unable to continue participating in the study. Any subject can completely withdraw her consent to participate in the study at any time during the study. The investigator will discuss with the subject the most appropriate way to withdraw to ensure the subject's health. Any subject who completely withdraws their consent to participate in the study will not receive further investigational treatment and / or study observations immediately after the date they request it.

Partial withdrawal of consent means that the subject does not want to continue being treated with the investigational product but still wishes to collaborate by remaining in the study to provide additional data (eg, participating in all subsequent study visits or procedures). Subjects may waive continuing to receive the investigational product at any time during the study. These subjects, in addition to those who have stopped receiving the investigational product for other reasons (eg, decision of the investigator or sponsor) should continue with the study observation program.

Reasons for withdrawal of the investigational product or observation may include:

Withdrawal of consent from the patient

Progressive disease

Intolerable toxicity

Investigator's decision based on what he considers best for the patient

If a subject (or her legally authorized representative) requests or decides to withdraw from the study, every effort should be made to complete and report the observations as widely as possible until the withdrawal date. All information must be included in the corresponding data collection notebooks.

8.7.2 Replacement of subjects

Subjects who withdraw from the study after inclusion will not be substituted. This study will include approximately 170 subjects.

9. Collection, registration and notification of security data

9.1 Definitions

9.1.1 Adverse events

In the International Conference on Harmonization (ICH) for Good Clinical Practice, an AE is defined as "any undesirable medical experience in a patient or clinical research subject treated with a pharmaceutical product and that does not necessarily have a causal relationship with its treatment". (ICH E6: 1.2).

The progression of the disease itself is not considered an adverse event. However, signs and symptoms of disease progression can be recorded as adverse events or serious adverse events. Death due to disease progression during the study should be reported on the death reports page of the data collection notebook, indicating the type of primary tumor as the reason for death.

Worsening of a pre-existing condition (eg, diabetes, migraine headaches, gout) should also be considered an AE if there is an increase in disease severity, frequency, or duration or an association with significantly worse outcomes.

Interventions for pretreatment disorders (eg, elective cosmetic surgery) or medical procedures planned prior to study inclusion are not considered AE.

The investigator is responsible for analyzing laboratory test results and determining whether an abnormal value in a particular study subject represents a change from pre-study values. In general, abnormal laboratory results of no clinical significance (at the discretion of the investigator) should not be recorded as EA; however, changes in laboratory values that require treatment or adjustment from previous treatment will be considered AE.

9.1.2 Serious adverse events

A serious adverse event (SAE) is defined as an AE that

It is mortal.

It is life-threatening (implies an immediate risk of death for the subject).

It requires the hospitalization of the patient or the prolongation of the existing hospitalization.

It results in a persistent or significant disability / incapacity.

It is a congenital anomaly / birth defect.

Another significant medical risk.

A hospitalization that meets the regulatory definition of "severe" is any admission of a patient to the hospital that includes a minimum stay of one night in a healthcare facility. Any AE that does not meet the definitions of severe (eg, accident and emergency department visit, outpatient surgery, or need for urgent study) may be classified as SAE if the investigator considers that it qualifies for "other risk". significant physician ". Examples include allergic bronchospasm, seizures, and blood dyscrasias.

Hospitalization to perform the procedures required by the protocol (or for elective procedures that have been scheduled before inclusion and that are not an exclusion criterion) or the administration of the study treatment is not classified as SAE.

9.1.3 Unexpected adverse event (not listed)

An unexpected AA, the nature or severity of which does not correspond to the information regarding the product.

As all the products administered in this trial are marketed in Spain and are used within the authorized conditions of use, the reference documents to establish the expectancy of adverse events will be the updated technical sheets available at:

<https://sinaem4.agemed.es/consaem/fichasTecnicas.do?metodo=detalleForm&version=new>

In the case of Cetuximab, the information from the latest version of the Investigator's Manual should also be taken into account..

9.1.4 Adverse Drug Reaction (AR) and Serious Adverse Reaction (RAG)

Any harmful and accidental response to a medical product related to any administered dose. The term "response to a drug" means that, at a minimum, a causal relationship between the drug and the adverse event would be a reasonable possibility, that is, the relationship cannot be ruled out. A severe RA (RAG) is an RA that meets the definition of severe (provided in point 9.1.2).

9.2 Reporting procedures for all adverse events

The investigator is responsible for ensuring that all AE (as defined in section 9.1) observed by the investigator or reported by the subjects are correctly recorded in the subjects' medical records, with one exception: those that occur before inclusion and that, furthermore, the researcher does not consider related to the study selection process.

In addition, the investigator is responsible for ensuring that, for subjects included in the study and receiving study treatment, all adverse events recorded in the subjects' medical records (as specified above) are reported in the CRD.

The investigator should record the following attributes of the AE: diagnosis or syndrome (s) of AE (if known; otherwise signs or symptoms), description of the event (with adequate detail for the event), onset dates, and resolution, severity, evaluation of the relationship with the treatment under study and measures taken. The investigator may be required to provide follow-up information, discharge reports, and extracts from medical or CRD records.

If applicable, the relationship of AE to the study treatment will be determined with the following question: "Is there a reasonable possibility that the event may have been caused by the study treatment?" The investigator should answer this question with "Yes" or "No".

If AE has occurred after informed consent but before the start of study treatment, the relationship of AE with the study selection process should be assessed by asking: "Is there a reasonable possibility that the event may have occurred due to the study selection process? " The researcher should answer this question with "yes" or "no". If the answer is yes, it should be recorded which part of the study selection is suspected.

The severity rating scale used in this study is described in Appendix C.

Medically significant AE that the investigator or sponsor considers related to the investigational product will be monitored until resolution or until they are considered stabilized.

It will be up to the investigator's clinical judgment to determine whether an AE is related and severe enough to require removal of the subject from treatment or study. A subject may also voluntarily abandon treatment for what he personally perceives to be intolerable AE. If either of these two situations occurs, the subject should be strongly encouraged to undergo an end-of-study evaluation and remain under medical supervision until symptoms cease or disorder stabilizes.

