A change from CT to MRI (or vice versa) of the liver is considered the only acceptable modality change and should not preclude assessment of response if, in the judgment of the center radiologist, there are no significant differences in assessment when changing modalities. This can occur if a subject is medically contraindicated for IV contrast. for CT during the trial. This change would require the prior approval of the developer. CT and MRI are the best and most reproducible methods currently available to measure selected index lesions for response assessment.

Ultrasound should not be used for the evaluation of visceral injuries. However, it is a possible alternative to clinical measurements of palpable superficial lymph nodes, subcutaneous lesions, and thyroid nodules or to confirm the complete disappearance of superficial lesions normally evaluated by clinical examination.

Study treatment (FOLFOX6 (m) / FOLFIRI (m) chemotherapy + biweekly cetuximab) will be discontinued in subjects with PE confirmed by RECIST criteria v.1.1 and will be followed up for safety (after at least 30 days since the last study drug administration).

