Single-arm, multicenter, prospective phase II clinical trial for biomarker validation in patients with advanced and / or metastatic colorectal cancer with non-mutated KRAS gene treated with chemotherapy plus biweekly cetuximab as first-line therapy

the quarterly lists of serious adverse reactions as provided by the R.D. 223/2004 and the GCP.

The sponsor will be responsible for preparing and submitting to the regulatory authorities and CEIC the annual safety reports of the trial, complying with what is specified in R.D. 223/2004 and the GCP. In addition, the sponsor will provide the Cetuximab producing Laboratory with a copy of the annual safety report when it is sent to the competent Health Authorities, as well as to the Clinical Research Ethics Committees.

The sponsor will notify the Clinical Research Ethics Committee and the competent health authorities of any new significant risk to patients as necessary.

The study sponsor is responsible for reporting all suspected serious adverse drug reactions (SARs) that occur in subjects exposed to the cetuximab product to the Merck safety representative in Spain on a regular basis (at least 6 months apart). Merck may request tracking information from the developer.

All serious adverse reactions associated or possibly associated with cetuximab and their follow-up reports should be sent to the Merck safety representative in Spain at the same time as they are sent to the regulatory body, the IRC or the CEIC. Within 24 hours of such shipment, a copy of any safety notification concerning the drug cetuximab must be faxed to the regulatory body, CRI or CEIC. The sponsor will be responsible for ensuring that the latest investigator's manual and technical sheet are used as the source document to determine the expected results of an SAE.

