6.5.1.2. Secondary endpoints

- Serum and tumor tissue secondary biomarkers evaluated to predict acquired chemo-resistance including BRAF and PI3K.
- ORR was defined as the incidence of a complete or partial response according to the revised RECIST 1.1 criteria.
- DoR (calculated only for the subjects who present an Overall Response): Time from the first assessment of Overall Response to radiologically-confirmed PD according to the revised RECIST 1.1 criteria. For subjects who showed response and did not show progression, DoR was censored on the last date of assessable disease evaluation reported in the eCRF of the study.
- OS: Time from the signature of the ICF date to date of death. For subjects who did not die or were lost to follow-up on the closing date for data analysis, OS was censored on the date of last contact.
- Safety: Type, frequency, and intensity of AEs related to the combination treatment.

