Pat. #	Hospital	Reason for exclusion from efficacy analysis	Valid for safety

Table 9. Response Rates (efficacy population) based on BRAF status

Best Response	N= all patients (%)	N= wt-BRAF (%)	N= mutant-BRAF (%)
Complete response (CR)			
Partial response (PR)			
Stable disease (SD)			
Disease Progression (PD)			
Not evaluable (NE)			
Overall response			
Disease Control Rate			

Figure 1. Progression free-survival

Progression free survival (PFS) based on the analysis of X patients showed a median of X (95% CI: X - X) months.

Figure 2. Overall survival

When OS was evaluated, an estimated median of X (95% CI: X - X months was reported.

The median OS of wt-BRAF patients was X (95% CI: X - X) months and for that of mutant BRAF patients was X (95% CI: X - X months (adjusted HR:X, CI 95% X- X; p-value=X).

Table 10. General toxicity profile (AEs+SAEs+SUSARs)

Adverse event	Any grade	Grade 3	Grade 4	Grade 5
	N (%)	N (%)	N (%)	N (%)

Table 12. Toxicity profile post treatment beginning (AEs+SAEs+SUSARs)

Adverse event	Any grade	Grade 3	Grade 4	Grade 5
	N (%)	N (%)	N (%)	N (%)

Table 13. Toxicity profile post treatment beginning related to treatment (AEs+SAEs+SUSARs)

Adverse event	Any grade	Grade 3	Grade 4	Grade 5
	N (%)	N (%)	N (%)	N (%)

Table 14. Toxicity profile post treatment beginning related to treatment with Cetuximab (AEs+SAEs+SUSARs)

Adverse event	Any grade	Grade 3	Grade 4	Grade 5
	N (%)	N (%)	N (%)	N (%)

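### Protocol 9.2 records causality once, for the combined treatment, and the SAP names no source or rule for Table 14 (toxicity related to cetuximab)

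*Protocol*

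**What the plan says.** Protocol 9.2 lists the attributes to record for each adverse event. The one that concerns causality is "evaluation of the relationship with the treatment under study and measures taken". For events on treatment it is settled by a single question, "Is there a reasonable possibility that the event may have been caused by the study treatment", answered yes or no. For events between consent and first dose, the same section has a parallel question about the selection process and then adds: "If the answer is yes, it should be recorded which part of the study selection is suspected". On-treatment events have no matching item asking which drug is suspected.

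Protocol 8.6 (tumour response evaluation) shows what study treatment means: "Study treatment (FOLFOX6 (m) / FOLFIRI (m) chemotherapy + biweekly cetuximab) will be discontinued" on confirmed progression. The safety endpoint is framed the same way. SAP 6.5.1.2 gives it as "Type, frequency, and intensity of AEs related to the combination treatment", and Protocol 10.2.2 agrees.

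Among the table shells in SAP section 7, Table 13 is toxicity after treatment start related to treatment. Table 14 is "Toxicity profile post treatment beginning related to treatment with Cetuximab (AEs+SAEs+SUSARs". The SAP does not say which variable separates the two.

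Protocol 9.4 requires drug-level identification for one class of event: "All serious adverse reactions associated or possibly associated with cetuximab" must be forwarded to the manufacturer's safety representative.

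**The concern.** The safety profile of cetuximab 500 mg/m² every 2 weeks is a secondary objective (Protocol 4.6.2, SAP 5.2). The trial has one arm, so no chemotherapy-only group exists against which background toxicity could be set. A table of cetuximab-related toxicity during combination therapy therefore depends on a causality judgement made per drug. The written collection rule does not ask for one.

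If Table 14 is filled from the rule as written, readers will see chemotherapy toxicity labelled as cetuximab toxicity. If it is filled by sorting events later, the attribution will come from someone other than the assessing investigator, by a rule that neither document states.

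**Working it through.** No figure in the plan bears on this point, so there is nothing to reproduce. The check compares what is collected with what is tabulated.

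**What is collected.** For an on-treatment event, let C mean a reasonable possibility that cetuximab caused it, and B the same for the chemotherapy backbone. The Protocol 9.2 item records R = (C or B).

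**What is tabulated.** Table 13 needs R = yes. Table 14 needs C = yes.

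**What R says about C.**

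| Recorded R | Possible (C, B) | Is C known? |
|---|---|---|
| No | (no, no) | Yes: C = no |
| Yes | (yes, no), (no, yes) or (yes, yes) | No |

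The single item therefore gives Table 14 only an upper bound: every cell lies between zero and the matching cell of Table 13. Taking R as a stand-in for C makes the two tables identical. For example, a neuropathy put down to oxaliplatin, a diarrhoea put down to irinotecan and a rash put down to cetuximab are all recorded as yes, and nothing in the item distinguishes them.

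**Where C can be recovered from other provisions.**

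1. *Serious reactions.* Protocol 9.4 requires those associated or possibly associated with cetuximab to be identified and sent on. Some cetuximab attribution should therefore exist for them, although 9.4 names no form or field. Table 14 also covers non-serious events.
2. *Cetuximab monotherapy.* Under Protocol 5.1, patients without progression after 6 months of chemotherapy continue on cetuximab alone, and those who stop chemotherapy early may do so. For events starting then, R = yes points largely to C = yes. The split is approximate, because delayed chemotherapy toxicity can carry over.
3. *Everything else.* Non-serious events during combination therapy, which may last up to 6 months, cannot be split by drug from the data that the protocol specifies.

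**Whether another planned step would reveal the problem.** SAP Table 3 lists grade and the need for SAE communication as the adverse-event variables for source data verification. Causality is not listed. SAP Table 7 likewise has one row for treatment-related toxicity as a reason for stopping, not split by drug.

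**The case against.** The strongest reply is that the forms are missing from the documents. Data go into an eCRF (Protocol 12.3.2) and serious events into a separate log (Protocol 9.3). Protocol 9.2 gives the wording of the question and does not forbid asking it once per drug. The SAP already reports results, such as AUCs and biomarker group sizes, so its authors may have known that a per-drug field existed when they laid out two tables. This stands, and it is why the conclusion is conditional. A reader might infer that Table 14 cannot be derived at all, or that it will certainly charge chemotherapy toxicity to cetuximab. The documents support neither: a per-drug field is neither shown nor excluded, and two classes of event can be separated without one.

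A second reply is that investigators distinguish the drugs anyway. Protocol 9.1.4 defines a reaction by the link between drug and event. Protocol 7.1.11 handles chemotherapy delays and cetuximab delays separately, 7.2.3 mentions skin toxicity unrelated to cetuximab, and 8.3 mentions toxicity due to the chemotherapy regimen. This shows that the judgement is made. It does not show that it is recorded as causality for each event, and a recorded measure taken is an action rather than an attribution.

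A third reply is that the endpoint is toxicity of the combination, which Table 13 delivers, with Tables 10 and 12 giving toxicity whatever the cause. That is correct and limits the importance of the point.

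A reader might also try to size the effect from the grade 3-4 percentages in the biweekly irinotecan plus cetuximab series cited in Protocol 4.3. That does not work. The event types may overlap within patients, so the percentages should not be added. The series gives no attribution by drug, and SAP Tables 13 and 14 are laid out by type of event, with no pooled total.

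**Conclusion.** The point holds as a conditional mismatch between collection and output. Protocol 9.2 specifies only a combined yes/no item, and the SAP gives no source field or rule for Table 14. If the eCRF has no per-drug causality field, Table 14 cannot be produced as labelled for non-serious events during combination therapy. If it does have one, what remains is a missing statement in the SAP.

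No numerical size can be given. Safety is secondary and descriptive, one table shell is affected, and the primary endpoint, its sample size and its analysis are untouched. The severity is minor. The conclusion assumes that study treatment in Protocol 9.2 has the meaning shown in Protocol 8.6, and that no per-drug rule exists in a document not supplied.

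**What to change.** Word the Protocol 9.2 causality item, and the matching eCRF field, separately for cetuximab and for the chemotherapy backbone, with yes or no for each and both allowed. State in the SAP that Table 14 is built from the cetuximab answer. If the eCRF already holds such a field, naming it and giving the rule is enough.

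The SAP gives June 2017 as study completion, so for this trial the choice probably lies in the reporting. If only the combined answer was collected:

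- delete Table 14, or relabel it and restrict it to events with documented cetuximab attribution;
- label Table 13 as related to the combination;
- show Table 13 separately for the combination and cetuximab monotherapy periods, noting that delayed chemotherapy toxicity may carry over;
- limit the safety conclusion to the combination.

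The cost is one extra tick-box per adverse event if changed prospectively, or the loss or relabelling of one descriptive table plus a split of another by period. Allowing both answers means that many events may still be marked for both components. That would be the investigator's recorded judgement, which the single item cannot supply.

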9.3 Reporting procedures for serious adverse events

The SAEs will be collected and recorded throughout the study period, starting from the signing of the informed consent until 30 days after the last dose of the investigational product or the end of the study (including the follow-up period) if this is produced later. All SAEs recorded in the subjects' medical records (as specified above) must be reported to the study sponsor within 1 business day of discovery or notification of the event. The initial SAE information and all modifications or additions should be recorded in a Serious Adverse Event Data Collection Log and faxed to the sponsor.

SAEs will also be collected and reported within 1 business day of discovery or notification of the event if it appears > 30 days after the last dose of the investigational product or after the end of the study and if it is believed to be possibly related with the investigational product. In all cases of death, available autopsy reports and relevant medical reports should be faxed to the sponsor. For this reporting process, subject assessments must be made 30 days or more after the last dose of the investigational product has been administered. The determination of whether an adverse event is expected will be based on the contents of the investigator's manual and the technical data sheet for the products marketed. If a subject is permanently withdrawn from the study due to an SAE, this information should be recorded on the initial or follow-up SAE notification form and on the end-of-study CRD.

The researcher must notify: GEMCAD Technical Secretariat.

The telephone and fax number of the contact person:

GEMCAD Technical Secretariat

[REDACTED]

9.4 Notification of adverse events to the regulatory agencies and the CEICs involved.

The sponsor will assume the responsibility of the adequate communication of the AA to the regulatory authorities.

The sponsor will expeditiously communicate all AAGs that are unexpected and associated with the use of the study treatment (SUSAR) to the researchers, to the clinical research ethics committees (CEIC) in accordance with the regulations in force (unless the CEICs require and document other measures), to the corresponding AEMPS and CCAA.

The sponsor will be responsible for making and submitting to the regulatory authorities and CEIC

Single-arm, multicenter, prospective phase II clinical trial for biomarker validation in patients with advanced and / or metastatic colorectal cancer with non-mutated KRAS gene treated with chemotherapy plus biweekly cetuximab as first-line therapy

the quarterly lists of serious adverse reactions as provided by the R.D. 223/2004 and the GCP.

The sponsor will be responsible for preparing and submitting to the regulatory authorities and CEIC the annual safety reports of the trial, complying with what is specified in R.D. 223/2004 and the GCP. In addition, the sponsor will provide the Cetuximab producing Laboratory with a copy of the annual safety report when it is sent to the competent Health Authorities, as well as to the Clinical Research Ethics Committees.

The sponsor will notify the Clinical Research Ethics Committee and the competent health authorities of any new significant risk to patients as necessary.

The study sponsor is responsible for reporting all suspected serious adverse drug reactions (SARs) that occur in subjects exposed to the cetuximab product to the Merck safety representative in Spain on a regular basis (at least 6 months apart). Merck may request tracking information from the developer.

All serious adverse reactions associated or possibly associated with cetuximab and their follow-up reports should be sent to the Merck safety representative in Spain at the same time as they are sent to the regulatory body, the IRC or the CEIC. Within 24 hours of such shipment, a copy of any safety notification concerning the drug cetuximab must be faxed to the regulatory body, CRI or CEIC. The sponsor will be responsible for ensuring that the latest investigator's manual and technical sheet are used as the source document to determine the expected results of an SAE.

